6.3.5 Removal of subjects

Every effort should be made to conduct all protocol-required procedures to complete the study. Participants may be removed from the study for the following reasons:

- Withdrawal of Consent: Participant wishes to exercise the right to withdraw from the study as stated in the ICF (all participants reserve the right to withdraw from the study without prejudice). We will still use the data obtained up until the time of withdrawal.
- Adverse Event: Participant experiences an adverse event that, in the investigator's opinion, necessitates withdrawal from the study.
- Investigator Decision: Investigator feels it is in the participant's best interest to terminate participation for reasons other than an adverse event.
- Protocol Violation: Participant is noncompliant with protocol procedures, violates study entry criteria, or starts an exclusionary concomitant medication. Examples of this include: started on > 1 gram of acetaminophen and/or hydroxyurea by the primary medical/surgical team while wearing the CGM sensor
- Administrative Reason: The study sponsor or other regulatory authority discontinues the study protocol or the clinical study site discontinues participation.

Any withdrawal must be fully documented in the participant's source records and recorded on the disposition page of the CRF. The documentation must include the reason for the withdrawal

and details of any sequelae (followed until symptoms resolve or improve, as appropriate). Withdrawals due to an adverse event must be documented on both the disposition page and the adverse event page of the CRF.

6.3.6 Statistical Design

The design is a randomized, open-label study. In order to reduce bias we propose stratified randomization per ward, whereby separate randomization lists will be developed for each individual ward.

The Dexcom G6 Pro CGM sensor will store four measurements per hour. If each subject remains in the study after sensor placement for a minimum of 48 hours, each subject will have 192 glucose measurements and a minimum of 4 postmeal periods of data. We will discard data from the first 12 hours after sensor placement given concerns about data accuracy during this time period, leaving a minimum of 144 measurements/subject. As the CGM will be placed the afternoon prior to starting the prandial insulin dosing, we anticipate that discarding the first 12 hours of data will have minimal impact on the study.

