5.2.1 Secondary and Exploratory Outcome Variables

All SG values collected by CGM during the hospital stay, analyzed as detailed above in Section 4.3 of the Study Objectives. Insulin doses given in each group will be analyzed. Demographic information including age, sex, race, BMI, reason for hospitalization, creatinine, HbA1c and medications prior to hospitalization.

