6.1 Method of Assignment/Randomization

This is an open-label, 1:1 randomized trial. Treatment assigned will be determined by the study team through computer-generated randomization.

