6.2 Assessments

The following assessments will be completed during the study:

Medical History: Study staff will obtain a prior history of diabetes and outpatient diabetes treatment medications. For women of non-childbearing potential, the reason should be documented.

Demographic/Medical information: Age, sex, BMI, vitals and reason for hospitalization will be obtained from the medical chart. Patients will be asked their self-identified race/ethnicity (white, black, Hispanic/Latino, Asian, or other). The most recent HbA1c if obtained during the index hospitalization or within 3 months prior to hospitalization will be collected from the medical chart. The serum creatinine at the time of randomization will be collected from the hospital record (note: serum creatinine is routinely obtained on all individuals admitted for inpatient care as part of the standard of care).

Blood Glucose Values/use of CGM: For insulin adjustment and treatment and monitoring of hypoglycemia, the standard hospital point of care meter will be used. At randomization a Dexcom G6 Pro CGM will be placed by the study team on the skin of the upper arm of the subject to collect blinded SG data during the study. The tiny sensor is under the skin and measures the interstitial glucose level, which is the glucose found in the fluid between the cells. The CGM device will be removed at the end of the study and the SG data from CGM will be used to assess glycemic outcomes.

If at any time the CGM becomes dislodged, a new device will be placed by the study team as soon as possible. If the patient must undergo a test during the study such as a CT scan or MRI where the CGM cannot be worn, the study team will remove the CGM prior to the test and place a new one as soon as possible immediately after the test.

Patient Reported Outcome (PRO) questionnaire: Study subjects will be asked to complete a questionnaire at the completion of the study (after sensor removal and before discharge). This questionnaire will assess the subject's perception of wearing a CGM device in the hospital and will also screen for adverse effects from wearing the CGM.

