6.3.3 Recruitment and Enrollment

Recruitment: Subjects will be recruited by reviewing the list of inpatients with diabetes from Epic. The study team will review the patient's sex, age, medical history, medications, ability to speak English or Spanish and BMI from Epic Systems Corporation (EPIC) medical records. Patients meeting the study criteria will be introduced to the study by a clinician who may also be an investigator. These patients will be screened in-person by the study team.

Enrollment: Participants are enrolled in the study when they have signed the ICF. Patients who enroll will receive \$25 dollars per day of participation, with a maximum of \$75 per subject. Payment will occur via ClinCard (a reloadable debit card), which subjects will receive after the consent process. After completion of participation, the study coordinator will add \$25 to the card for each day of participation up to a maximum of \$75. At the onset of the study, participants will be enrolled on 4 regular inpatient floors only (Menino building floors 6 East, 6 West, 7 East, 7 West), but this will be expanded to all other regular med-surg inpatient floors and stepdowns after the recruitment of 10 participants OR two months from study onset (whichever occurs first).

During the study: Please refer to section 5.1 General Design Description for a detailed review of what will happen once patients are recruited in the study.

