6.3.7.1 Primary Analyses

The percentage of time spent in various glycemic target range will be calculated as the number of measurements in each glycemic range divided by the total number of recorded measurements. We will compare the percentage of time spent in range (100-180 mg/dL, both inclusive) in the postprandial period using Student t tests, among those randomized to NovoLog® vs. Fiasp®. Non-inferiority of Fiasp® can be confirmed if participants randomized to Fiasp® demonstrate <5% lower amount of time spent in glycemic target range compared to NovoLog®.

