6.3.7.2 Secondary Objectives Analyses

We will compare percentage of time spent in other ranges of interest as detailed in the Study Objectives using Student t tests between NovoLog® vs. Fiasp® groups. We will explore other demographic factors in modeling procedures (including age, sex, and BMI) using analysis of covariance.

In additional sensitivity analysis, we will repeat all analysis using only data from the first three meals for each patient in order to partially account for differences in hospitalization duration.

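### The primary non-inferiority t test uses neither the ward stratification nor the baseline data already collected; it is valid, but may be less precise than a pre-specified adjusted model

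*Combined protocol and SAP*

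**What the plan says.** Section 6.3.6 sets up the allocation: "In order to reduce bias we propose stratified randomization per ward, whereby separate randomization lists will be developed for each individual ward". Section 6.1 says only that "Treatment assigned will be determined by the study team through computer-generated randomization"; it mentions neither strata nor blocks. The number of strata is open. Section 6.3.3 starts on four floors and adds that "this will be expanded to all other regular med-surg inpatient floors and stepdowns after the recruitment of 10 participants", or after two months if that comes sooner.

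The primary analysis in 6.3.7.1 compares postprandial time in range "using Student t tests, among those randomized to NovoLog® vs. Fiasp", with nothing else in the model. Adjustment appears only under the secondary analyses (6.3.7.2): "We will explore other demographic factors in modeling procedures (including age, sex, and BMI) using analysis of covariance". That list is open-ended, and 5.2.1 uses the term broadly: "Demographic information including age, sex, race, BMI, reason for hospitalization, creatinine, HbA1c and medications prior to hospitalization". HbA1c and prior therapy could therefore enter the exploratory model. Ward is named in neither place.

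The baseline data will exist. Section 6.2 says: "The most recent HbA1c if obtained during the index hospitalization or within 3 months prior to hospitalization will be collected", and also: "Study staff will obtain a prior history of diabetes and outpatient diabetes treatment medications".

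**The concern.** When allocation is stratified on a factor that predicts outcome, the between-ward variation is balanced by design, yet an unadjusted t test still counts it as noise. The same applies to any prognostic baseline variable left out of the model. The result is not bias or an inflated error rate. It is an interval that may be wider than the data require, compared with a 5-point margin.

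HbA1c and prior therapy are natural candidates on the protocol's own logic. Both enter eligibility (inclusion criterion 6), HbA1c enters the starting-dose table in 5.1, and one dosing route there carries on the patient's existing insulin.

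The lost precision matters only if the SD of 10 is too low. Section 6.3.7 concedes that no source exists for the SD of this endpoint in this population. The exploratory model's covariates are also not fixed, and the trial is open-label, so an adjusted result chosen later would carry little weight.

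**Working it through.** **Inputs from 6.3.7:** margin 5 points, SD 10, one-sided alpha 0.025, true difference 0, power 80%, 63 per group required for non-inferiority, 80 per group planned. R², the share of outcome variance explained by ward and covariates, is not in the documents. It is an assumption, taken from 0 to 0.30.

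**1. The plan's own figure.** n per group = 2 × [10 × (1.960 + 0.842) / 5]² = 62.8, so 63. This reproduces.

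**2. The planned t test at 80 per group.** SE = 10 × √(2/80) = 1.581. Half-width = 1.96 × 1.581 = 3.10. Power = Φ(5/1.581 − 1.96) = Φ(1.202) = 88.5%. With the t distribution these become 3.12 and 88.2%.

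**3. The SD at which power is 80%.** 5 / [√(2/80) × 2.802] = 11.3.

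**4. Ideal effect of adjustment.** Multiply the SE by √(1 − R²), and divide the 80%-power SD by the same factor.

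| R² (assumed) | Half-width (SD 10) | Power (SD 10) | SD giving 80% power |
|---|---|---|---|
| 0 | 3.10 | 88.5% | 11.3 |
| 0.05 | 3.02 | 90.1% | 11.6 |
| 0.10 | 2.94 | 91.5% | 11.9 |
| 0.20 | 2.77 | 94.2% | 12.6 |
| 0.30 | 2.59 | 96.6% | 13.5 |

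At R² = 0.20 the gain equals 80/(1 − 0.20) = 100 per group analysed without adjustment.

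**5. If the SD is larger (assumed values).** Power at R² = 0, 0.10, 0.20 and 0.30:
- SD 12: 75.0%, 79.3%, 83.8%, 88.3%
- SD 15: 55.9%, 60.3%, 65.4%, 71.2%

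**6. Ward alone, by simulation.** 160 patients, SD 10, true difference −5, 4,000 runs per setting. The number of wards and the block size of 4 are assumptions. Each cell gives the half-width for the t test, then for the model with fixed ward terms.

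| Setting | Wards explain 0% | 5% | 10% |
|---|---|---|---|
| 4 wards, blocked | 3.12, 3.12 | 3.10, 3.04 | 3.08, 2.96 |
| 12 wards, blocked | 3.12, 3.13 | 3.11, 3.05 | 3.10, 2.96 |
| 12 wards, unblocked | 3.12, 3.24 | 3.12, 3.17 | 3.11, 3.08 |

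Blocked lists gain about 2% at 5% explained and 4 to 5% at 10%. Unblocked lists with 12 fixed ward terms change the width by about +3.8%, +1.5% and −1.0%.

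**7. Ward plus two covariates, by simulation.** With 12 unblocked wards pooled to 4, the half-width went from about 3.12 (t test) to 3.07, 2.91 and 2.72 at total R² of 0.10, 0.20 and 0.30. It widened by less than 2% when nothing was prognostic. The gain is smaller than in step 4 because that formula charges nothing for lost degrees of freedom or chance imbalance, and pooling discards some of the between-ward signal.

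**8. Validity.** Across two sets of simulations with blocked ward lists, the one-sided error of the t test at the margin was 0.017 to 0.026 (Monte Carlo standard error about 0.0025). That is at or slightly below the nominal 0.025.

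**The case against.** The best case for leaving the plan alone is that nothing in it is wrong. An unadjusted test after stratified allocation is legitimate, and the stated reason for stratifying is to reduce bias, not to gain precision. On the plan's own figures power is 88.5% against a target of 80%. Section 6.3.7 also says the SD was deliberately set above what is expected and that no advantage of Fiasp was assumed. Ward alone gains little, and unblocked lists with many fixed ward terms can widen the interval. The larger gains rest on an assumed R², and HbA1c brings a missing-value rule that the t test does not need.

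Much of this stands. The point concerns efficiency only, ward by itself is a minor contributor, and the table in step 4 is optimistic. It does not remove the case for change. The SD is called conservative without a source, and power reaches 80% at an SD only 1.3 points above the assumed value. Pooling or a random ward effect limits the possible widening, and step 7 shows a gain under unfavourable allocation once the covariates carry some information. The exploratory covariance analysis does not fill the gap, because its covariates are not fixed and it is not primary.

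Separately, 6.3.7.1 does not tie its 5% rule to a confidence limit. The figures here assume that it will be.

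**Conclusion.** The concern holds as a matter of precision. The t test keeps its error rate, and at an SD of 10 with 80 per group the trial is adequately powered without adjustment. A pre-specified adjusted model would plausibly narrow the half-width from about 3.1 points to between 2.7 and 3.1 for R² between 0.10 and 0.30, with pooled wards and unblocked lists. It gains nothing, and may widen the interval by up to about 2%, if the covariates are not prognostic. The benefit is mainly protection against an SD above 11.3; it would not rescue a much larger one (at SD 15 and R² = 0.30, power is still only 71.2%). These figures rest on the assumed R², on the assumed number of wards, and on non-inferiority being judged by a 95% interval. The change is advisable, not essential.

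**What to change.** In 6.3.7.1, make the primary analysis a linear model of postprandial percentage time in range on treatment, ward, HbA1c and pre-admission insulin use (yes/no), and compare the lower limit of the two-sided 95% interval for Fiasp minus NovoLog with −5 points. Pool small wards by a rule stated in advance, or fit ward as a random effect. State how missing HbA1c is handled, since it is recorded only where a result exists. Keep the unadjusted t test as a sensitivity analysis. In 6.1, state the ward stratification so that it matches 6.3.6, and say whether the ward lists are blocked and how.

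This covariate set is a proposal; what matters is that one set is fixed before outcome data are analysed. The cost is SAP wording, two rules (ward pooling and missing HbA1c) and one model. No new data are needed.

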6.3.7 Sample Size Considerations

Although our primary objective is to assess the non-inferiority of our intervention, we calculated power based on our secondary analysis in which we assess the superiority of our intervention because a much lower sample size is required for the non-inferiority analysis given our anticipated results.

Powering non-inferiority of our primary outcome: Using a one-sided (alpha=0.025) power calculation, we estimate that we would need a sample size of 63 participants per group to have 80% power to detect non-inferiority of Fiasp® compared to NovoLog® in postmeal time in glycemic range (100-180 mg/dl), assuming we set our non-inferiority margin at 5% less time in glycemic range and a standard deviation of 10%. A 5% non-inferiority margin was set according to an international consensus report stating that changing time in range by 5% increments would be clinically relevant. It is important to note that we have no true reference for a standard deviation of postmeal time in range for our study population, so we chose a conservative (higher than expected) standard deviation. These calculations are also conservative because they assume no hypotheses about superiority of Fiasp® (using sealedenvelope.com to calculate power).

We also estimated requiring only 63 participants to have 80% power (alpha=0.05) to detect a 2.5% greater time in glycemic range (superiority) for participants randomized to Fiasp®, compared to NovoLog® (with a 5% standard deviation of the outcome), however, we expect a greater change in percent time in range.

We will be sufficiently powered for non-inferiority (and superiority) of our primary outcome because we have chosen to power our study in order to be able to execute our secondary analysis, described below.

Powering for secondary analysis: We estimate that 80 participants per group will provide 80% power (alpha=0.05, two sided) to detect a 20 mg/dL difference in mean 24 hour (day 2) glucose between groups, assuming a standard deviation for mean glucose of 45 mg/dL, which was reported previously in a study of inpatient prandial insulin dosing (16). Previous intervention studies using CGM have reported larger differences (treatment vs. control) for time in target

glycemic range compared to differences in mean glucose (17), and we also expect larger differences (treatment vs. control) for glucose variability. Therefore, we expect to have greater power to detect differences in our primary outcome (percentage of time in the glycemic target range) because these measures have proved to be a sensitive measure of glycemic control which leverage the full granularity of CGM data (18, 19).

We anticipate that we will need to screen 210 patients to randomize 89 participants per group in order to achieve a sample size of 80 participants per group (expecting a 15% screen fail rate and a 10% rate of drop out or early hospital discharge).

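### Section 6.3.7 uses SD 10% for non-inferiority but an unexplained SD 5% for superiority on the same outcome, and its claim of sufficient superiority power at 2.5 points depends on the 5%

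*Combined protocol and SAP*

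**What the plan says.** All of this is in section 6.3.7 (Sample Size Considerations).

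- **Non-inferiority, postmeal time in range 100-180 mg/dL.** One-sided alpha 0.025 and 80% power give 63 per group, "assuming we set our non-inferiority margin at 5% less time in glycemic range and a standard deviation of 10" per cent. The section admits that "we have no true reference for a standard deviation of postmeal time in range for our study population". It answers that gap by taking a value it describes as cautious, that is, above what it expects. It justifies the margin by citing a consensus view that "changing time in range by 5% increments would be clinically relevant".
- **Superiority, same outcome.** "We also estimated requiring only 63 participants to have 80% power (alpha=0.05) to detect a 2.5% greater time in glycemic range (superiority", this time "with a 5% standard deviation of the outcome". The sentence closes: "however, we expect a greater change in percent time in range". The larger change is not quantified, and nothing is said about why the SD is now 5%.
- **What sets the trial size.** A 20 mg/dL difference in mean 24-hour glucose with SD 45 mg/dL, two-sided alpha 0.05 and 80% power gives 80 per group.
- **The conclusion drawn.** "We will be sufficiently powered for non-inferiority (and superiority) of our primary outcome because we have chosen to power our study" for that secondary analysis. The closing paragraphs add that larger differences are expected in time in range than in mean glucose, so power should be greater. They attach no SD and no effect size to this.

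**The concern.** An outcome has one SD in a given population. If none is known and 10% is the cautious choice for non-inferiority, the reader needs to know why 5% is suitable for superiority. The section does not say.

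The two answers of 63 hide the change. They agree only because the difference and the SD are halved together, so both calculations have a standardised difference of 0.5. At any common SD, detecting 2.5 points needs four times the sample needed for a 5-point margin with a true difference of zero.

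The sentence on sufficient power then carries the superiority claim forward without a difference or an SD, and supports it with a calculation on another endpoint. Superiority on postprandial time in range is the hypothesis in section 4.1 and the first-named secondary objective in section 4.3. A reader should be able to see what 80 per group can and cannot detect on that outcome.

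**Working it through.** **Inputs, all from section 6.3.7 unless noted.** Non-inferiority: margin 5, SD 10, true difference 0, one-sided 0.025. Superiority: difference 2.5, SD 5, alpha 0.05. Mean glucose: difference 20, SD 45, two-sided 0.05. Power is 80% throughout. The test is Student's t (section 6.3.7.1). Percentages are read as percentage points of time. The sidedness of the superiority test is not stated; two-sided reproduces 63, whereas one-sided gives 50.

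**Step 1: reproduce the plan.** n per group = 2 × (1.960 + 0.8416)² × (SD/difference)² = 15.698 × (SD/difference)².

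- Non-inferiority: 15.698 × (10/5)² = 62.8, so 63.
- Superiority: 15.698 × (5/2.5)² = 62.8, so 63. This is per group, which the text omits.
- Mean glucose: 15.698 × (45/20)² = 79.5, so 80.

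All three agree with the plan. Using the t distribution instead gives 63.8, 63.8 and 80.4, an immaterial change.

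**Step 2: one common SD.**

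- SD 5%: non-inferiority 15.698 × (5/5)² = 15.7, so 16; superiority at 2.5 points, 63.
- SD 10%: non-inferiority 63; superiority at 2.5 points, 15.698 × (10/2.5)² = 251.2, so 252.

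**Step 3: power with 80 per group.** Two-sample t test, two-sided 0.05 for superiority and one-sided 0.025 for non-inferiority. SD 5% and 10% are the plan's values; 7.5% and 15% are assumed here to show the range.

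| SD | Superiority, 2.5 points | Superiority, 5 points | Non-inferiority, margin 5, true difference 0 |
|---|---|---|---|
| 5% | 88% | >99% | >99% |
| 7.5% | 55% | 99% | 99% |
| 10% | 35% | 88% | 88% |
| 15% | 18% | about 55% | about 55% |

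**Step 4: limits.** At 80 per group, 80% power needs a standardised difference of 0.4457.

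- Smallest difference with 80% power: 0.4457 × 5 = 2.2, 0.4457 × 10 = 4.5 and 0.4457 × 15 = 6.7 points.
- Largest SD that keeps 80% power: 2.5/0.4457 = 5.6% for 2.5 points; 5/0.4457 = 11.2% for 5 points and for non-inferiority.
- If all 89 randomised per group were analysed, these limits would be about 5.9% and 11.8%.

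**Step 5: does the mean-glucose calculation carry over?** Its standardised difference is 20/45 = 0.444. It supports a time-in-range claim only if the standardised time-in-range difference is also about 0.446 or more. At SD 10% that means about 4.5 points, not 2.5.

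**The case against.** The best defence is that the sentence should be read in context. The paragraph just before it gives the superiority inputs, 2.5 points and SD 5%. On those inputs 80 exceeds 63 and power is 88%, so the claim is true as calculated. The plan also says it expects more than 2.5 points, and at 5 points and its own SD of 10% the power is 88%. Calling 10% higher than expected implies that a lower value was thought likely, so a second calculation at a lower SD is not a contradiction. The closing argument about larger differences is worded as an expectation.

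Most of this stands. A reason is given for the 10%; only the 5% and the change between the two lack one. What the defence does not supply is a basis for 5% when the section says no reference exists, or a figure for the larger change. Nor does it show that the claim holds under the SD the plan itself chose as conservative. For 2.5 points it does not.

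**Conclusion.** The point holds as a minor fault in the stated assumptions. The superiority part of the power claim is true at 2.5 points only if the SD is 5.6% or less, and the plan's other SD for the same outcome is 10%. At that value, power for 2.5 points is 35% and 252 per group would be needed for 80%. These figures assume 80 analysed per group and a two-sided 0.05 t test.

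A reader might infer more than the documents support:

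- **That the trial is expected to have 35% power for superiority.** It is not. That figure pairs the conservative SD with a difference the plan expects to exceed.
- **That the sample size is wrong.** The plan's figures reproduce, and non-inferiority power is 88% at SD 10%.
- **That power is safe across the board.** That does not follow either. No reference SD exists, so 10% is not a ceiling. At an assumed 15%, power for non-inferiority and for 5-point superiority is about 55%.
- **That a non-significant result rules out 2.5 points whenever the SD is 5.6% or less.** The confidence interval decides that, not planning power. At SD 5.6% the 95% half-width is about 1.75 points, so an estimate of 1.5 reaches 1.5 + 1.75 = 3.25 and does not exclude 2.5. At SD 10% the half-width is about 3.1, so an estimate of -1 reaches about 2.1 and does exclude it.

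**What to change.** Use the same SD, at least the plan's 10%, in both time-in-range calculations. Replace the sentence on sufficient power with conditional figures, for example:

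> No reference SD is available for postmeal time in range in this population. An SD of 10% is assumed for both non-inferiority and superiority; it is not an upper limit. At this SD, 80 per group gives 88% power for non-inferiority (5-point margin, true difference zero), 88% for superiority if the true difference is 5 points, and 35% if it is 2.5 points. The smallest difference with 80% power is about 4.5 points. At an SD of 15%, power for non-inferiority and for 5-point superiority would be about 55%.

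Write 63 per group in the superiority calculation. Keep the argument about larger differences in time in range as an expectation, not as support for the power figures. State that a non-significant superiority result will be interpreted from its confidence interval.

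The cost is a rewording of section 6.3.7, and the stated superiority power becomes less favourable. Sample size and analysis stay as they are. This version is dated 11/11/2022 and section 7.15 expected data collection to finish by the end of 2022, so the gain is in how the result is read, not in the design.

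### The assurance of sufficient, and even greater, superiority power for postprandial time in range is unsupported; the 80% at 80 per group applies to 24-hour mean glucose only

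*Combined protocol and SAP*

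**What the plan says.** Section 4.3 makes superiority on time in 100–180 mg/dL over the 4-hour postprandial periods the lead secondary objective, and Section 4.1 hypothesises superior postprandial control. Section 6.3.7 (Sample Size Considerations) then does four things.

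- It sizes the trial on a different measure. The target of 80 per group, with 80% power at a two-sided 5% level, is set "to detect a 20 mg/dL difference in mean 24 hour (day 2) glucose between groups". The SD used there is 45 mg/dL, taken from a published inpatient study.
- It says the trial is sufficiently powered for both non-inferiority and superiority of the primary outcome, because it was sized for that secondary analysis. It goes further after noting that earlier CGM studies reported larger differences for time in range than for mean glucose: "Therefore, we expect to have greater power to detect differences in our primary outcome (percentage of time in the glycemic target range". It adds that time in range is a sensitive measure that uses the full detail of the CGM record.
- It gives one direct superiority calculation for time in range: "We also estimated requiring only 63 participants to have 80% power (alpha=0.05) to detect a 2.5% greater time in glycemic range (superiority"). This calculation takes the SD of time in range to be 5 points, and the plan remarks that the true change should exceed 2.5 points.
- In the preceding paragraph it sizes non-inferiority on the same outcome, "assuming we set our non-inferiority margin at 5% less time in glycemic range and a standard deviation of 10" percent, for 63 per group. There it says that it has no true reference for this SD in the study population.

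**The concern.** Power depends on the difference divided by its own SD. That earlier studies showed larger differences in time in range says nothing about power unless the SD is known too, and none is given with that argument. The appeal to CGM detail is also doubtful: under Section 6.3.7.1 each reading counts only as inside or outside the range, so how far outside is lost.

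The 80% for mean glucose therefore cannot be carried over to time in range, still less improved upon. The study hypothesis is tested by this superiority comparison. If the assurance stays, a null result could be read as adequately powered evidence of no benefit when the design has not been shown to have that power.

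**Working it through.** **1. The plan's figures reproduce.** Normal approximation: n per group = 2(1.960 + 0.842)² / d², where d = difference / SD.

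- Mean glucose: d = 20/45 = 0.444; n = 79.5, so 80 per group. Power at 80 per group is 80.3% (79.8% with the noncentral t).
- Time in range, superiority: d = 2.5/5 = 0.50; n = 62.8, so 63 **per group** (79.5% by t). With 63 in total, 31.5 per group, power is 50%.
- Time in range, non-inferiority: margin/SD = 5/10 = 0.50, again 63 per group.

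**2. The plan's time-in-range inputs at 80 per group.** Power ≈ Φ(d√(80/2) − 1.960).

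| Difference | SD | d | Power at 80 per group |
|---|---|---|---|
| 2.5 points | 5 (superiority paragraph) | 0.50 | 88% |
| 2.5 points | 10 (non-inferiority paragraph) | 0.25 | 35% |

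At SD 10, 80% power for 2.5 points needs 252 per group. With 80 per group, the difference detectable with 80% power is about 2.2 points at SD 5 and 4.4 points at SD 10.

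**3. What an equal 20 mg/dL shift would mean for time in range.** The documents give 20, 45, the 100–180 band and 80 per group. They do not give the control mean, the within-patient spread or the shape of the distributions, so these are assumed and varied. For a patient with mean μ and within-patient SD s, the share in range is Φ((180.5 − μ)/s) − Φ((99.5 − μ)/s). Patient means have SD 45 in both groups, and the Fiasp mean is 20 lower.

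Worked case: control mean 200, s = 40, normal patient means. The total SD is √(45² + 40²) = 60.2.

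- Control: Φ(−19.5/60.2) − Φ(−100.5/60.2) = 32.5% in range.
- Fiasp, mean 180: Φ(0.5/60.2) − Φ(−80.5/60.2) = 41.3%.
- Difference 8.7 points. The between-patient SD of time in range, found numerically, is 22.7 points. So d = 0.385 and power is 68%.

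With s from 30 to 60 mg/dL or a within-patient CV of 20–35%, and normal or lognormal patient means, power at 80 per group is about:

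| Control mean (mg/dL) | Power |
|---|---|
| 160 | 5–14% |
| 180 | 38–54% |
| 200 | 64–79% |
| 210 | 69–74% normal; 76–83% lognormal |
| 220 | 70–76% normal; 80–85% lognormal |
| 240 | 66–77% normal; 82–85% lognormal |

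The ends move by a point or so with the grid chosen. At 160 with skewed means, time in range can even fall slightly, because the shift takes readings below 100.

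**4. Sensitivity to the model.** Skewed (lognormal) readings within patients lower the figure at 180 to about 21–35% (CV 20–35%, lognormal means). A proportional reduction averaging 20 mg/dL raises it: with lognormal means, about 55–66% at 180, 77–80% at 200 and up to 83% at 220; with normal means some cases pass 80% at 200. That is no longer the plan's 20/45 input, however. At 200 the treated SD falls to 45 × 0.9 = 40.5, so mean glucose gains as well: 20/√((45² + 40.5²)/2) = 0.467. Over a grid of 180 scenarios, d for time in range was below 0.444 in 161, including all with control mean 200 or less. The SD of time in range was about 9–36 points. Sampling noise from only 4–6 meals per patient is left out; it would lower power further.

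**The case against.** A reader might infer that the plan's own 20 and 45 mg/dL prove that superiority power for time in range is below 80%. The documents do not support this. The conversion needs a control mean, a within-patient spread and a distribution shape that they do not give, and some reasonable choices give 80–85%. Nor does the plan equate the two effects. The 20 mg/dL is a day-2, 24-hour mean, while time in range covers the 4 hours after meals, where a mealtime insulin could have a larger effect. For the same reasons no single replacement figure, such as 45–65%, belongs in the SAP.

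The plan also has its own time-in-range calculation, which gives 88% at 80 per group, and it expects more than 2.5 points. The arithmetic stands. It could be defended by reading 5% as the expected SD and 10% as the deliberately conservative one. But no source is given for 5%, and an assurance that moves from 88% to 35% between two adjacent paragraphs needs a justification.

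It is tempting to say that the plan compared percentage points with mg/dL. The text does not say whether the larger differences were raw, relative or standardised, so the claim can be called unsupported but a unit error cannot be shown.

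Nor do the stated inputs undermine non-inferiority: with SD 10% and no true difference, power at 80 per group is about 88%. The missing per group after 63 is editorial, since nobody would run this trial with 63 in total.

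**Conclusion.** The point holds as a matter of unsupported power statements, not of wrong arithmetic: every stated sample size reproduces. The 80% at 80 per group belongs to 24-hour mean glucose. For postprandial time in range, neither greater power nor sufficient superiority power has been shown.

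Two sizes matter. On the plan's own inputs, power for 2.5 points is 88% or 35%, depending on which of its two SDs is used; this needs no outside assumption. For an equal 20 mg/dL shift, power is below 80% in most scenarios, and in every fixed-shift scenario examined with a control mean of 200 mg/dL or less. It reaches about 80–85% only with skewed patient means at about 210 or more. This second result rests on the assumed control mean, spread and shape, and on treating the 24-hour and postmeal effects as equal.

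The consequence is confined to the secondary superiority test and how a null result there would be read.

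**What to change.** In Section 6.3.7:

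- Delete the inference to greater power, and the words that extend sufficient power to superiority of the primary outcome.
- State that 80 per group and 80% power refer to 24-hour mean glucose (20 mg/dL, SD 45 mg/dL) only.
- Use one SD for postprandial time in range in the non-inferiority and superiority calculations, or justify using two.
- Restate superiority power at 80 per group for a stated difference over a range of SDs; for 2.5 points, 88% at SD 5% and 35% at SD 10%. Do not insert a single converted figure.
- Correct the superiority sentence to 63 participants per group.

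The cost is wording only. Sample size, endpoints and analyses do not change. The stated superiority power becomes less favourable.
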